5.8 Blinding of Study Drug

Packages will be labeled with a lot number. Kits will be assigned a number 1-40 to indicate subject number, and will include 9 boxes, each labeled with the subject number, box number and lot number. Randomization will take place at the manufacturer. Forty sealed envelopes will be sent by the Institute of Ethnomedicine to study site, DHMC, for emergency unblinding. Unblinding information will be kept in the Investigational Pharmacy and accessible 24/7 in case of emergency unblinding.

5.9 Receiving, Storage, Dispensing and Return

5.9.1 Receipt of Drug Supplies

The L-serine will be shipped directly from Knechtel Laboratories to Dartmouth-Hitchcock Medical Center Department of Neurology, 4th Floor Research Offices, [name]. Upon receipt of the of the study treatment supplies, an inventory will be performed and a drug receipt log will be filled out and signed by the person accepting the shipment. The designated study staff will count and verify that the shipment contains all the items noted in the shipment inventory. Any damaged or unusable study drug in a given shipment (active drug or comparator) will be documented in the study files. The investigator will notify the Institute for Ethnomedicine of any damaged or unusable study treatments that were supplied to the site.

5.9.2 Storage

L-serine foil packages should be kept in a cool, dry location during storage and patients will be advised to keep their monthly packets in a cool, dry location.

5.9.3 Dispensing of Study Drug

The boxes of packets will be dispensed at study visits or shipped to the participant. Patients should return any unused packets or gummies and report compliance during study visits. The Dartmouth Hitchcock Investigational Pharmacy will keep record of all study drug issued and study drug returned by participants. Notation will also be made in the participants' electronic medical records regarding the dispensation and collection of the study medication.

5.9.4 Return or Destruction of Study Drug

At the completion of the trial, a final reconciliation of all study drug shipped, consumed and remaining will be performed. All remaining drug will be returned to the Institute for Ethnomedicine, [name].

6 Study Procedures

The study timeline includes four clinic visits and three telephone calls as well as one follow-up phone call that will occur at 0 weeks (30 days after the last clinic visit). The study visits and timeline are as follows:

6.1 Visit 1: Screening and Enrollment (Day 0)

- Obtain Informed Consent
- Clinical Dementia Rating Scale
- Brief review of medical history and demographic collection
- Neurological and physical exam
- Capture and grade baseline conditions
- Concomitant medication assessment
- Montreal Cognitive Assessment (MoCA)
- Blood Draw:
 - Safety Labs completed locally (BMP, CBC)
 - Hemoglobin A1C level
 - Samples sent to the Brain Chemistry Laboratories for L-serine levels and neurally-derived exosomes with optional excess blood set aside for future protein expression and RNA blueprints
- Review of Inclusion/Exclusion Criteria
- Randomization
- Dispense study medication, dosing instructions and calendar

6.2 Follow-Up Phone Call #1: Week 2

- Medication Compliance
- Adverse Events
- Concomitant Medications

6.3 Follow-Up Phone Call #2: Week 4

- Medication Compliance
- Adverse Events
- Concomitant Medications

6.4 Follow-Up Phone Call #3: Week 8

- Medication Compliance
- Adverse Events
- Concomitant Medications

6.5 Visit 2: Week 12 (+/- 2 weeks)

- Brief neurological and physical exam
- Review of adverse events
- Review current medications
- Blood Draw: Safety Labs completed locally and samples sent to the Brain Chemistry Laboratories for L-serine levels optional excess blood set aside for future protein expression and RNA blueprints at scheduled visit date or next in person visit if there are restrictions in place for in person visits
- Collect unused study medication and calendar at next in person visit
- Dispense study medication and calendar (may be shipped to the participant to be received at scheduled visit date)

6.6 Visit 3: Week 24 (+/- 2 weeks)

- Brief neurological and physical exam
- Montreal Cognitive Assessment, (MoCA)
- Review of adverse events
- Review current medications
- Blood draw: Safety Labs completed locally and samples sent to the Brain Chemistry Laboratories for levels and neurally-derived exosomes with optional excess blood set aside for future protein expression and RNA blueprints at scheduled visit date or next in person visit if there are restrictions in place for in person visits
- Collect unused study medication and calendar at next in person visitDispense study medication and calendar (may be shipped to the participant to be received at scheduled visit date)

6.7 Visit 4: Week 36 (+/- 2 weeks)

- Brief neurological and physical exam
- MoCA exam
- Review of adverse events
- Review current medications
- Blood draw: Safety Labs completed locally and samples sent to the Brain Chemistry Laboratories for L-Serine levels and neurally-derived

exosomes with optional excess blood set aside for future protein expression and RNA blueprints

- Collect unused study medication and calendar. If participant unable to do this in person due to restrictions in place, provisions will be made to assist participant to mail the study medication and calendar to the research team at no expense to the participant.

6.8 Follow-Up Study Coordinator Phone Call: 4 weeks (+/- 2 weeks) after Visit 4:

- Review of adverse events
- Continued supplementation status
- L-Serine Tolerability
- Overall study impression

At study conclusion, the data will be collected and analyzed. Unblinding of study participants will occur after final analysis of all data.

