3.1 General Design

This is a Phase IIa, randomized, double-blind, placebo controlled trial. Potential subjects for participation in this study will be identified by the Investigator based on their clinical and radiographic diagnosis of Alzheimer's disease, which will be completed as part of standard care. Up to 40 subjects will be enrolled. Subjects participating in the study will be randomized to receive either gummies containing L-Serine or placebo gummies, with the Investigator and study staff blinded to the group assignments. An individual subject's participation in the study will last approximately 40 weeks from time of enrollment. Study office visits will take place at Day 0, week 12, week 24 and week 36. Phone contact will be made at week 2, week 4 and week 8 to assess compliance, adverse events and concomitant medication. A follow-up phone call will also be made at week 40 to inquire about adverse events, concomitant medication, subject impression of study, subjective L-serine tolerability, and if they are continuing L-serine supplementation. If, due to study-related events, the PI judges that a participant should be seen in office during study participation, a visit will be scheduled (Unscheduled Visit)

The Day 0 visit includes subject consent, administration and scoring of the Clinical Dementia Rating Scale, review of medical history including any family history of Alzheimer's disease, a brief neurological and physical exam, capture and grading of baseline conditions, and a review of concomitant medications. Hemoglobin A1C, safety labs (CBC, BMP) and research only blood draw will be completed. Eligibility will be confirmed by the PI prior to randomization. If a participant fails to qualify based on their CDR score or Hgb A1 level, the portion of their blood drawn for research only will be discarded.

All subsequent study visits include a brief physical/neurological exam, adverse event assessment, study medication compliance assessment, concomitant medications review, safety blood draws (CBC, BMP) and research-specific blood draws.

Study medication will be dispensed at Day 0, week 12, and week 24, and collected at week 12, week 24 and week 36. All unused study drug will be collected and returned to the study sponsor.

The MoCA will be performed at Visits 0, week 24, week 36, and at early withdrawal or unscheduled visits. Three different MoCA versions will be administered in a random order during these assessments.

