4.4 Early Withdrawal: When and How to Withdraw Subjects

Participants taking NMDA receptor antagonist or Acetylcholinesterase inhibitor medications must be on a stable dose for 30 days prior to beginning the study. Participants may come off these medications during the course of the study if it is in their best interest, though should consult with the PI regarding this decision. Participants will be asked to refrain from starting NMDA receptor antagonist or Acetylcholinesterase inhibitor medications throughout the duration of this trial. If they wish to begin these therapies, they may opt to do so and be withdrawn from this clinical trial

Participants will be placed on an ascending dose for two weeks of 2 x 1g gummies BID, two weeks of 8 x 1g gummies BID, and then provided the target dose of 15 x 1g gummies BID for 36 weeks if they are able to tolerate these doses without negative effects. If a patient cannot tolerate 2 or 8g (BID) they will cease treatment. If a patient can tolerate 8g (BID) but not 15g (BID), they will remain in the study through the remainder of the study timeline taking a total of 15g per day (1 package of gummies split into two time periods within the day). The same escalating dose schedule and procedures will be observed for both placebo and L-serine patients. If a participant experiences an adverse event which is serious in nature, and deemed to be drug related, the study medication will be discontinued immediately. The Investigator may reserve the right to discontinue a subject from treatment if the PI feels it is not in the best interest of the participant to continue in the study.

If a participant discontinues study medication they will be encouraged to remain in the study and complete study related procedures and assessments while not receiving study medication.

If a participant discontinues study medication and does not wish to return for the remainder of study visits, this decision will be documented. They will be asked to return to the site for a final study visit. This visit will be conducted with the same study procedures and assessments as "Visit 4" listed in Section 6.5.

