The study period during which adverse events must be reported is normally defined as the period from the initiation of any study procedures to the end of the study treatment follow-up. For this study, the study treatment follow-up is defined as 30 days following the last administration of study treatment.

Preexisting Condition

A preexisting condition is one that is present at the start of the study. A preexisting condition should be recorded as an adverse event if the frequency, intensity, or the character of the condition worsens during the study period.

General Physical Examination Findings

At screening, any clinically significant abnormality should be recorded as a preexisting condition. Any new clinically significant findings/abnormalities that meet the definition of an adverse event must also be recorded and documented as an adverse event.

Post-study Adverse Event

All unresolved adverse events should be followed by the investigator until the events are resolved, the subject is lost to follow-up, or the adverse event is otherwise explained. At the last scheduled visit, the investigator should instruct each subject to report any subsequent event(s) that the subject, or the subject's personal physician, believes might reasonably be related to participation in this study. The investigator should notify the FDA of any death or adverse event occurring at any time after a subject has discontinued or terminated study

participation that may reasonably be related to this study. The FDA should also be notified if the investigator should become aware of the development of cancer or of a congenital anomaly in a subsequently conceived offspring of a subject that has participated in this study.

Abnormal Laboratory Values

Study lab results will be reviewed by the PI when results are available, prior to dispensation of the following visit study medication. The PI will make the determination of clinical significance of lab values that are out of normal range. Those of clinical significance will be reported as adverse events. No lab values are identified as exclusionary but the PI may withdraw a subject if they feel it is in the subject's best interest.

Hospitalization, Prolonged Hospitalization or Surgery

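### The final safety call need not cover the 30-day adverse event period in section 8.1, and no call is scheduled after an early-withdrawal visit

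*Combined protocol and SAP*

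**What the plan says.** Section 8.1 sets the length of the adverse event period: "For this study, the study treatment follow-up is defined as 30 days following the last administration of study treatment".

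The one planned contact after Visit 4 is a coordinator's phone call, and its timing is given in different ways:

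- Section 6.8: "4 weeks (+/- 2 weeks) after Visit 4".
- Section 6 introduction: "one follow-up phone call that will occur at 0 weeks (30 days after the last clinic visit". The zero looks like a truncated 40, and nothing here rests on it.
- Section 3.1: "A follow-up phone call will also be made at week 40 to inquire about adverse events". The grid agrees on week 40 and adds a window of 2 weeks either side.

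Section 6.7 has unused drug handed back at Visit 4: "Collect unused study medication and calendar. If participant unable to do this in person due to restrictions in place".

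For a patient who stops drug and does not want to continue visits, section 4.4 provides one more attendance: "They will be asked to return to the site for a final study visit". The grid's early-withdrawal column marks adverse event tracking at that visit and nothing after it.

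**The concern.** Section 8.2 ties active questioning about adverse events to contacts with the patient. Where no contact falls at or after day 30, nobody is scheduled to ask about the rest of the period. A coordinator could follow 6.8 exactly and still leave part of the 8.1 period without enquiry.

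Tolerability is named first in the section 2 objective. Uneven follow-up after the last dose would mean that events are sought for different lengths of time in different patients. The shortest follow-up would tend to fall on those who left early, a group that can include patients who left because they tolerated the gummies poorly. In a trial of at most 40 patients, a few missed events could be visible in the tolerability summary.

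**Working it through.** The plan states no figure for how much of the 30 days the call covers, so there is nothing to reproduce. The check is calendar arithmetic.

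**Inputs.** Adverse event period: 30 days after last dose (8.1). Call: 4 weeks ± 2 weeks after Visit 4 (6.8), or week 40 ± 2 weeks (grid), or 30 days from the final clinic visit (section 6 introduction). Visit 4: week 36 ± 2 weeks (6.7). Assumption: the last dose is on the day of Visit 4, which fits the return of unused drug there.

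1. **Call under 6.8.** 4 × 7 = 28 days; 28 − 14 = 14; 28 + 14 = 42. Shortfall = 30 − day of call. Nominal: 30 − 28 = 2 days (28/30 = 93% covered). Earliest: 30 − 14 = 16 days (14/30 = 47% covered).

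2. **How much of the window is short.** The window has 42 − 14 + 1 = 29 permitted days. Days 14 to 29 come before day 30: 29 − 14 + 1 = 16 of the 29.

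3. **If the last dose is L days before Visit 4.** The largest shortfall is 30 − (14 + L). L = 0 gives 16 days. L = 2 gives 14, and the nominal call then lands on day 30. L = 16 gives 0. So the whole window is adequate only if dosing stopped at least 16 days before Visit 4.

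4. **Call under the grid.** Visit 4: 252 ± 14 = days 238 to 266. Call: 280 ± 14 = days 266 to 294. If both windows run from Day 0, the interval from Visit 4 to the call is 266 − 266 = 0 days at the shortest and 294 − 238 = 56 days at the longest. This is wider than 6.8 in both directions.

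5. **Call under the section 6 introduction.** Day 30 exactly, shortfall 0. No window is given.

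6. **Early withdrawal with no further visits.** The documents do not say how long after the last dose the final visit takes place. If it is D days, the part of the period with no scheduled contact is 30 − D: 30 days for D = 0, 16 for D = 14, none for D ≥ 30.

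7. **When dosing ends.** The documents give three answers, and the 30 days would end at different times:

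| Source | Last dosing day | Period ends |
|---|---|---|
| Study Summary, 36 weeks of administration | 36 × 7 = 252 | 252 + 30 = 282 |
| Study Summary regimen and section 5.2, 28-day ramp plus 246 days | 28 + 246 = 274 | 274 + 30 = 304 |
| Section 4.4, 28-day ramp plus 36 weeks at target | 28 + 252 = 280 | 280 + 30 = 310 |

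The nominal week 40 call, on day 280, comes before all three. The grid's latest call, on day 294, comes before the last two.

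**The case against.** The strongest reply is that the call does not bring adverse event collection to an end. A reader might infer from the timing that events after it go unrecorded, but the documents do not support that. The 8.1 period is fixed by the last dose, whenever the call is made. Unresolved events are followed further, and section 8.3.1 makes unexpected, related events reportable to the IRB even after the study. What can be lost is active enquiry. At the nominal date that is 2 days, probably because 4 weeks and 30 days were treated as the same thing; the 16 days arise only at the edge of the window.

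A reader might also infer that everyone who stops early has none of the 30 days covered. That goes too far. Section 4.4 asks patients who stop drug to stay on for the remaining assessments, and those who do may be covered by later visits and the week 40 call. Zero coverage requires that a patient declines further visits and attends the final visit on the day of the last dose. Section 4.4.2 also follows patients terminated because of an adverse event until it resolves. The section 6 wording could be stretched to mean a withdrawal visit, though neither 6.8 nor the grid marks such a call.

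Nor is later reporting left solely to patients with memory impairment: section 8.1 also counts events that the patient's own physician thinks may be related.

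Finally, most tolerability information comes from the contacts at weeks 2, 4, 8, 12, 24 and 36, and the call schedule is the same in both arms. The call also asks about continued L-serine use, so the weeks after Visit 4 need not be free of L-serine.

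All of this stands, and it limits the size of the point. It does not supply a scheduled enquiry that reaches day 30. The provisions for known, unresolved or suspected-related events do not actively look for a new event that nobody has linked to treatment.

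**Conclusion.** The point holds as a mismatch between the stated adverse event period and the contacts meant to serve it. If the last dose is at Visit 4, active enquiry under 6.8 can stop 2 days early on the nominal date and up to 16 days early within the permitted window. The grid allows a wider spread, 0 to 56 days after Visit 4, if its windows run from Day 0. Patients who stop drug and decline further visits have no scheduled contact after the withdrawal visit; how much of the 30 days this leaves open depends on an interval that the documents do not state.

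The consequence is possible under-recording of late events in the tolerability assessment. The documents do not support a claim that reporting stops at the call, or that the arms are treated differently by design. The efficacy analysis is not affected. This is worth correcting because tolerability is a stated objective and the correction is cheap.

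**What to change.** Reconcile the section 6 introduction, 6.8, 8.1 and the grid so that the final call is timed from the last dose and cannot come before the end of the 30-day period that the protocol already states. Mark the same call in the grid for patients who withdraw early.

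At the same time, reconcile the end-of-dosing statements in the Study Summary, section 4.4 and section 5.2. Without that, the day of the last dose, and so the timing of the call, is not well defined. Which statement is right is for the sponsor to settle.

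The cost is a text and grid amendment and one extra phone call per early withdrawal. Some calls also move later, by about two weeks at most under 6.8 (30 − 14 = 16 days for a call that would have been made at the start of the window).

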6.9 Blood Draws and Specimen Processing, Storage and Shipment

Safety labs will be drawn at four time points: Visit 1 (Baseline/enrollment), Visit 2, Visit 3 and Visit 4. Blood draws may be delayed and obtained at a later date (next in person visit due to restrictions placed on participant in person visits by Dartmouth-Hitchcock or the participant).

Safety labs include:

- Complete Blood Count
- Liver Function Test
- Basic Metabolic Panel

Blood samples will be drawn and sent to the Brain Chemistry Laboratories for analysis of L-Serine levels and neurally-derived exosomes at four time points: Visit 1 (Baseline/enrollment), Visit 2, Visit 3 and Visit 4 which may include delays in obtaining due to participant unable to attend the visit at the scheduled date

6.10 Optional Blood Donation

There will be an option in the consent for patients to have a portion of their blood drawn to be saved and used for future use by the Institute of Ethnomedicine. The researchers at the Brain Chemistry Laboratories wish to utilize the optional

donations to possibly evaluate for protein expression and corresponding RNA blueprints. These exploratory evaluations will not be reported back to patients. No extra blood is required for the blood donation. Opting in is not required for study participation.

7 Statistical Plan

7.1 Sample Size Determination

In a previous study (Fiandaca, 2014), the neurally derived blood exosomal beta-amyloid protein level of eAD patients had a standard deviation of 2.8 pg/ml. The minimum detectable difference in the means of the treatment and placebo subjects is 2.5 pg/ml, with power 0.8 ($\alpha = 0.05$). An increase of approximately 7 pg/ml was observed between preclinical AD and AD patients (Fiandaca, 2014).

Based on Nasreddine et al. (2005), the standard deviation of the MoCA is approximately 4 points. Power calculations suggest that the minimum detectable difference in mean MoCA scores for two groups, each with 20 patients, is 3.65 points. A similar result for sample size comes from Mead's resource equation to predict adequate sample size, e.g. $E = N - B - T$, where N is the required sample size, E is the degrees of freedom of the error component (usually around 20), B is the blocking component for environmental effects, and T is the number of Treatments plus controls,

Placebo: 20 patients

L-serine: 20 patients

Total treatments: 2

Total patients: 40

Subtracting one degree of freedom from each value before inserting it in the equation, we have $E = 39 - 1 - 1 = 37$, Understanding that individual patients may drop out of the study before the 36 week dosing completion for various reasons, this sample size will be adequate to provide the needed statistical power.

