7.2 Statistical Methods

Nonparametric statistics are proposed since it is not known in advance if MoCA scores or levels of neurally-derived exosomes will approximate, or can be transformed, to a normal distribution. A Mann-Whitney U-test will compare exosomal protein levels or MoCA scores between the L-serine treatment and placebo patients at a $p < 0.05$ level. Parametric equivalents will be considered if appropriate to the distribution of the data.

First, we will check the effectiveness of the randomization by comparing the baseline characteristics of the L-serine and placebo groups according to demographic factors (e.g. age, gender). We will also assess whether the levels of biomarkers or cognitive impairment in the treatment group differ from the placebo group at time zero. This first test will check whether the randomization procedures were sufficient for the study. Next we will compare the exosomal protein levels or MoCA scores at the last study visit (month 9). (H_0 = there is no difference between the median exosomal protein level or MoCA score for treatment patients and control patients; H_1 = there is a difference between the median exosomal protein level MoCA score for treatment patients and control patients). A Mann-Whitney U-test will examine exosomal protein levels or MoCA scores of each patient, by comparing median values between groups. Second, we will assess the slope of the exosomal protein levels or MoCA scores over time to see if they differ among the treatment and control groups by Mann-Whitney U-test. We will use Spearman's Rank correlation, in which rho is the equivalent of the parametric correlation coefficient, to determine if there is a monotonic relationship between levels of proteins in the neurally-derived exosomes and the MoCA scores.

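### Section 7.1 calls 40 patients adequate despite dropout, but its 3.65-point MoCA figure already uses all 20 per arm, and Mead's equation adds no support.

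*Combined protocol and SAP*

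**What the plan says.** Section 7.1 takes a MoCA standard deviation of about 4 points and states: "Power calculations suggest that the minimum detectable difference in mean MoCA scores for two groups, each with 20 patients, is 3.65 points". For exosomal beta-amyloid, with SD 2.8 pg/ml, it states: "The minimum detectable difference in the means of the treatment and placebo subjects is 2.5 pg/ml, with power 0.8", at alpha 0.05. No group size is attached to that second figure, and no alpha or power to the first.

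It then introduces Mead's resource equation with the words "A similar result for sample size comes from", notes that the error degrees of freedom E are usually around 20, and obtains E = 39 - 1 - 1 = 37. The last sentence of the paragraph foresees losses before week 36 but still concludes that "this sample size will be adequate to provide the needed statistical power". This is the only statement about dropout in Section 7. No rate, inflation factor or evaluable number is given.

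Other relevant places:

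- Section 3.1 caps enrolment at 40, and Section 5.3 provides 20 kit numbers per arm. Replacement of patients is not described.
- Section 3.2 names both the week-36 MoCA score and the slope from Day 0 to week 36. Section 7.2 tests both by Mann-Whitney, starting with the scores at month 9.
- Section 4.4 withdraws patients who start certain Alzheimer's drugs. It encourages patients who stop study drug to stay for assessments, and asks those who leave to return for a final visit.

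**The concern.** The section gives a detectable difference tied to exactly 20 patients per group, and then credits the same 20 per group with tolerance for dropout. Both hold only if the calculation kept something in reserve. If 3.65 is simply what 20 complete patients per arm can detect, any missing week-36 score makes it optimistic. Mead's equation sits directly before the adequacy sentence and reads as independent confirmation, so it matters whether it confirms anything.

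At stake is how the result is read. Someone interpreting a null finding, or sizing a later trial from this one, would take 3.65 points as a sensitivity that survives attrition.

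**Working it through.** **Inputs.** MoCA SD 4, beta-amyloid SD 2.8 and 20 per arm come from Section 7.1. Alpha 0.05 and power 0.80 are stated there for beta-amyloid and assumed here for MoCA. Two-sided testing is inferred from the non-directional alternative hypothesis in Section 7.2. Losses of 10% and 20% (18 and 16 evaluable per arm) are assumptions.

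**1. Reproducing 3.65.** For a two-sample t-test, the noncentrality is d / (SD × √(1/n₁ + 1/n₂)) on n₁ + n₂ - 2 degrees of freedom. With n = 20 per arm the standard error is 4 × √0.1 = 1.265, and d = 3.65 gives 3.65 / 1.265 = 2.886 on 38 df. The critical value is 2.024 and power is 80.3%. Solving for 80% power gives d = 3.64; solving for n at d = 3.65 gives 19.86 per arm. The alternatives fit worse: the normal approximation gives (1.960 + 0.842) × 1.265 = 3.54, a one-sided t-test at 80% gives 3.20, and a two-sided t-test at 90% gives 4.21. So the plan's figure is the t-test result with every patient evaluable.

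**2. Effect of missing scores on a one-time-point MoCA comparison.** The Mann-Whitney columns are simulated with normal data, exact critical values and ties ignored.

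| Evaluable per arm | t-test power at 3.65 | t-test detectable difference (80%) | Mann-Whitney power at 3.65 | Mann-Whitney detectable difference |
|---|---|---|---|---|
| 20 and 20 | 80.3% | 3.64 | about 78% | about 3.74 |
| 20 and 19 | 79.2% | 3.69 | – | – |
| 19 and 19 | 78.1% | 3.74 | – | – |
| 18 and 18 | 75.8% | 3.85 | about 73% | about 3.98 |
| 16 and 16 | 70.5% | 4.09 | about 67% | about 4.25 |

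The t-test detectable difference rises by 3.85 - 3.64 = 0.21 points at 18 per arm. At 16 it rises by about 0.46 (4.095 - 3.637 before rounding).

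**3. Beta-amyloid, SD 2.8.** At 20 per arm the t-test detects 2.55 pg/ml and the normal approximation 2.48. Both round to the stated 2.5, so the method behind it cannot be identified, but neither leaves a reserve at 2.5. At 20, 18 and 16 per arm, t-test power at 2.5 is 78.6%, 74.0% and 68.6%. The detectable difference is 2.55, 2.69 and 2.87 by t-test, and about 2.62, 2.79 and 2.98 by Mann-Whitney.

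**4. Mead's equation.** Using the plan's own subtraction, (N - 1) - 1 - 1 = 20 gives N = 23. The plan inserts N = 40 and gets 37, well above the value it calls usual. Nothing in the equation refers to SD, effect size, alpha, power or dropout. With 23 patients (12 and 11), t-test power at 3.65 points is 55%.

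**5. The slope.** Treat it as a simple change from Day 0 to week 36 with SD 4 at both visits and correlation r. The SD of change is then 4 × √(2(1 - r)).

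| r | SD of change | t-test detectable difference at 20, 18, 16 per arm |
|---|---|---|
| 0.3 | 4.73 | 4.30, 4.55, 4.84 |
| 0.5 | 4.00 | 3.64, 3.85, 4.09 |
| 0.7 | 3.10 | 2.82, 2.98, 3.17 |

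The detectable difference stays at or below 3.65 only if r is at least about 0.50, 0.55 or 0.60 respectively. The documents give no r and no SD of change.

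**The case against.** The strongest reply is that 3.65 is a detectable difference, not a requirement. The plan names no target MoCA effect, so the power it needs is undefined and the adequacy sentence cannot be shown false. That stands: the sentence is unsupported, not refuted.

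Several further points also carry weight:

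- **The SD is only approximate.** At SD 3.9, 19 per arm still detects 3.64; at SD 4.1, even 20 per arm has only 78.3% power. One lost patient costs about one percentage point, less than this uncertainty, so 80% should not be treated as a cliff. The 10% and 20% losses cost 4.5 and about 10 points.
- **The planned test may do better if the data are not normal.** With t (5 df) tails at the same SD, Mann-Whitney power at 3.65 is about 86%, 82% and 76% at 20, 18 and 16 per arm. The deficit in the table depends on normality.
- **The normal approximation tolerates one loss per arm** (80.3% at 19). However, that formula gives 3.54 at 20 per arm, not the plan's 3.65.
- **The slope is also part of the primary endpoint** and may be more precise. It may equally be less precise; its reserve is unknown.
- **Retention is addressed.** Section 4.4 keeps patients who stop drug under assessment, and Section 3.1 and the Timeline of Events schedule a MoCA at week 24 and at early withdrawal. This may limit missing scores, but nothing says how an early score enters the month-9 comparison.
- **The beta-amyloid point is narrow.** The plan reports: "An increase of approximately 7 pg/ml was observed between preclinical AD and AD patients". That gap is not a treatment effect, but at half of it, 3.5 pg/ml, t-test power is still 93% with 16 per arm. The missing reserve is at 2.5 only.

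The scale also counts: this is a small proof-of-concept trial, and a modest loss of power is no reason to redesign it.

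**Conclusion.** The concern holds. The 3.65-point figure is the t-test result with all 40 patients evaluable, and 40 is the most the design can enrol, so for a one-time-point comparison it contains no allowance for dropout. At assumed losses of 10% and 20%, t-test power at 3.65 falls from 80.3% to 75.8% and 70.5%, and the detectable difference rises to 3.85 and 4.09 points. Mead's equation does not give a similar result and cannot support the adequacy claim.

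This rests on SD 4, on two-sided alpha 0.05 and 80% power carried over to MoCA, and on normal data for the Mann-Whitney figures. It does not extend to the slope comparison, and it does not show that the trial is too small for its purpose, since no target difference is named. It should be corrected because the plan claims a property that its own calculation lacks.

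**What to change.** Delete the Mead argument and the adequacy sentence from Section 7.1. Replacement text could read:

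> No allowance for dropout is built into the sample size. Assuming normally distributed values, 80% power and two-sided alpha 0.05, the detectable week-36 MoCA difference (SD 4) is about 3.6 points by t-test (about 3.75 by Mann-Whitney) with 20 evaluable patients per arm, 3.85 (about 4.0) if 10% have no week-36 score (18 per arm), and 4.1 (about 4.3) if 20% have none (16 per arm). For exosomal beta-amyloid (SD 2.8) the corresponding figures are about 2.55 (2.6), 2.7 (2.8) and 2.9 (3.0) pg/ml. These figures do not apply to the slope comparison.

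If the sponsor has an expected loss rate, it should replace the illustrative 10% and 20%.

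The cost is text only. The stated detectable differences become slightly less favourable, and the change itself alters no patient numbers, procedures or tests.
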